⁸ Standard physical examination including oral cavity and oropharynx. A symptom driven examination can be performed at other time, at Investigator or designee's discretion.

⁹ Symptom driven and if deemed necessary.

¹⁰ Symptom driven and if deemed necessary based on the follow-up call. Subjects will visit the clinic for this to take place.

¹¹ Body weight only at Start of Week -1

¹² Body weight only at end of study

STUDY EVENTS/ASSESSMENTS	Screening ¹	Clinic Visits					Out-of-CRU Between Clinic Visits		
		Start of Week -1	End of Week -1 (baseline)	End of Week 2	End of Week 4	End of Week 6			
Clinical Chemistry ¹³ , Hematology, Urinalysis	X							X	
Urine Drug and Alcohol Screen	X	X	X	X	X	X		X	
HIV, HBsAg, and HCV Serology	X								
Serum Pregnancy Test (females)	X								
Serum FSH Test ¹⁴	X								
Urine Cotinine Screen	X	X							
Exhaled CO Measurement	X	X							
Test Product (VLN cigarette) Trial	X								
Provide Smoking Cessation Information ¹⁵	X							X	X
Review of AEs	X ¹⁶	X	X	X	X	X		X	X
Urine Pregnancy Test (females)		X	X						
Review Restrictions on Smoking and Nicotine Product Use	X	X	X	X	X	X			
Reminder Contacts to return to the CRU ¹⁷		X ¹⁸					X ¹⁹		
Test Product Dispensing			X	X	X				

¹³ Clinical chemistry tests will be performed after at least an 8 hour fast; however, in case of dropouts or rechecks, subjects may not have fasted for 8 hours prior to the clinical chemistry sample being taken.

¹⁴ Postmenopausal females only

¹⁵ Subjects will be referred to the Quit Assist® website

¹⁶ AE recording to begin immediately after the product trial at Screening.

¹⁷ Phone calls or texts or instant messages (as per site preference) reminding subjects of clinic visits.

¹⁸ The day prior to clinic visit at start of Week -1 subjects will be contacted.

¹⁹The day prior to clinic visits at end of Weeks -1, 2, 4 and 6 subjects will be contacted.

STUDY EVENTS/ASSESSMENTS	Screening ¹	Clinic Visits					Out-of-CRU Between Clinic Visits		
		Start of Week -1	End of Week -1 (baseline)	End of Week 2	End of Week 4	End of Week 6			
Dispense Canisters for Used Cigarette Butt Collection		X	X	X	X				
Used Cigarette Butt Collection							X		
Used Cigarette Butt Canister Return			X	X	X	X			
24-hour Urine Collection for BoE analysis			X	X		X			
Plasma Sample for Cotinine Analysis			X	X		X			
Blood Sample for COHb Analysis			X	X		X			
Puffing Topography ²⁰			X	X		X			
Blood Samples for Nicotine PK Analysis ²¹			X	X		X			
Training on e-diary use		X							

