5. STUDY PROCEDURES

5.1 Screening

Potential subjects will undergo Screening procedures to ensure that they meet the requirements for inclusion in the study within 28 days prior to their first study visit at the start of Week -1.

Screening procedures will include the following:

- Sign ICF
- Demographics
- Smoking/tobacco/nicotine product use history
- UB cigarette and flavor documentation, including taking a color photocopy of the front and back of the subject's UB cigarette pack along with a ruler
- Medical history
- Review of Concomitant Medications
- Standard physical examination including oral cavity and oropharynx
- Review of Inclusion/Exclusion criteria
- Clinical laboratory tests (clinical chemistry, hematology, urinalysis)
- HIV, HBsAg, and HCV serology
- Urine drug and alcohol screens
- Exhaled breath CO measurement
- Urine cotinine screen
- Vital signs
- Height, body weight, and BMI
- 12-lead ECG
- Serum pregnancy test for females
- Serum FSH for postmenopausal females
- Review of smoking and nicotine product restrictions
- VLN cigarette trial
- Begin AE recording after product trial
- Provide smoking cessation information

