5.10 Product Trial

At screening, subjects will have an opportunity to smoke 2-3 VLN cigarettes over a 1-hour period to ensure that they can tolerate smoking those cigarettes for a period of 6 weeks. The number of cigarettes smoked will be documented, as will any abnormal events (e.g., excessive coughing) during the product trial. Subjects who react negatively (*i.e.*, unwilling to use and/or cannot tolerate the product [experience adverse events (AEs) that will prevent them from continuing to use the product as judged by the Investigator]) to the VLN cigarettes during the product trial period will not continue in the study.

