6.4 Safety

All clinical safety data will be listed by subject and time point as appropriate. The following items will be summarized using n, arithmetic mean, SD, median, minimum, and maximum for continuous data and frequency counts for categorical data.

- Subject disposition
- Subject demographics
- Tobacco product use history

- Vital signs

All events captured in the database will be listed in by-subject data listings. However, only study product use-emergent AEs will be summarized. A study product use-emergent AE is defined as an AE that is starting or worsening at the time of or after the first study product use (i.e., Product Trial).

Frequencies of subjects with study product use-emergent AEs, regardless of relationship to study product will be summarized and sorted by system organ class. Frequencies of subjects with study product use-emergent serious AEs will be likewise summarized. Frequencies of study product use-emergent AEs will be summarized by severity and relationship to study product.

Changes in physical examinations (if any) will be described in the text of the final report. All concomitant medications recorded during the study will be listed by subject.

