Table 12-1 Adverse Event Frequency - Number of Subjects Reporting the Event (% of Subjects Used Product)

[figure not shown]
Adverse Events*	Baseline	VLN Non-Menthолated	VLN Menthолated	UB Non-Menthолated	UB Menthолated	Overall#
Number of Subjects Used Study Product	XX (100%)	XX (100%)	XX (100%)	XX (100%)	XX (100%)	XX (100%)
Number of Subjects With Adverse Events	X (XX%)	X (XX%)	X (XX%)	X (XX%)	X (XX%)	X (XX%)
	X (XX%)	X (XX%)	X (XX%)	X (XX%)	X (XX%)	X (XX%)
General disorders and administration site conditions	X (XX%)	X (XX%)	X (XX%)	X (XX%)	X (XX%)	X (XX%)
Vessel puncture site pain	X (XX%)	X (XX%)	X (XX%)	X (XX%)	X (XX%)	X (XX%)
Vessel puncture site reaction	X (XX%)	X (XX%)	X (XX%)	X (XX%)	X (XX%)	X (XX%)

*Adverse events are classified according to MedDRA® Version 21.0
Subjects used their own usual brand cigarettes at Week -1.
Although a subject may have had 2 or more clinical adverse experiences, the subject is counted only once within a category. The same subject may appear in different categories.
Overall includes AEs after the start of Week1 product use.

Source: Table 14.3.1.1
Program: /CAXXXXX/sas_prg/stsas/intexttest/t_ae.sas DDMMYY HH:MM

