Musculoskeletal pain	X (X%)	X (X%)	X (X%)	X (X%)	X (X%)	X (X%)
Nervous system disorders	X (X%)	X (X%)	X (X%)	X (X%)	X (X%)	X (X%)
Headache NOS	X (X%)	X (X%)	X (X%)	X (X%)	X (X%)	X (X%)

Note: *Adverse events are classified according to MedDRA Version 20.0. ^ = Product-use-emergent adverse events
 Subject used their usual brand at Baseline (Week -1).

VLN non-mentholated = Non-mentholated VLN cigarettes

VLN mentholated = Mentholated VLN cigarettes

UB non-mentholated = Subjects' UB non-mentholated filtered cigarettes

UB mentholated = Subjects' UB mentholated filtered cigarettes

Overall includes AEs after the start of Week1 product use.

Program: /CAXXXXX/ECR/sas_prg/stsas/tab prgrname.sas DDMMYYYY HH:MM

Post-text Table 14.3.1.2 will be in the following format:

Page 1 of X

Table 14.3.1.2 Product-Use-Emergent Adverse Event Frequency -
 Number of Adverse Events (% of Total Adverse Events) (Safety Population)

Adverse Event*	Baseline	VLN Non- Mentholated	VLN Mentholated	UB non- Mentholated	UB Mentholated	Overall#
Number of PUEAEs	XX (XXX%)	XX (XXX%)	XX (XXX%)	XX (XXX%)	XX (XXX%)	XX (XXX%)
Eye disorders	X (X%)	X (X%)	X (X%)	X (X%)	X (X%)	X (X%)
Vision blurred	X (X%)	X (X%)	X (X%)	X (X%)	X (X%)	X (X%)
Gastrointestinal disorders	X (X%)	X (X%)	X (X%)	X (X%)	X (X%)	X (X%)
Dyspepsia	X (X%)	X (X%)	X (X%)	X (X%)	X (X%)	X (X%)
Nausea	X (X%)	X (X%)	X (X%)	X (X%)	X (X%)	X (X%)
Musculoskeletal and connective tissue disorders	X (X%)	X (X%)	X (X%)	X (X%)	X (X%)	X (X%)
Back pain	X (X%)	X (X%)	X (X%)	X (X%)	X (X%)	X (X%)
Muscle cramps	X (X%)	X (X%)	X (X%)	X (X%)	X (X%)	X (X%)
Musculoskeletal pain	X (X%)	X (X%)	X (X%)	X (X%)	X (X%)	X (X%)
Nervous system disorders	X (X%)	X (X%)	X (X%)	X (X%)	X (X%)	X (X%)
Headache NOS	X (X%)	X (X%)	X (X%)	X (X%)	X (X%)	X (X%)

Note: *Adverse events are classified according to MedDRA Version 20.0. ^ = Product-use-emergent adverse events
 Subject used their usual brand at Baseline (Week -1).

VLN non-mentholated = Non-mentholated VLN cigarettes

VLN mentholated = Mentholated VLN cigarettes

UB non-mentholated = Subjects' UB non-mentholated filtered cigarettes

UB mentholated = Subjects' UB mentholated filtered cigarettes

Overall includes AEs after the start of Week1 product use.

Program: /CAXXXX/ECR/sas_prg/stsas/tab prgrname.sas DDMMYY HH:MM

Post-text Table 14.3.1.3 will be in the following format:

Page 1 of X

Table 14.3.1.3 Product-Use-Emergent Adverse Event Frequency by Severity and Relationship to Study Product -

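### AEs from the screening VLN product trial are emergent under the protocol, but the SAP excludes them from Overall and does not define where else they are counted

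*SAP*

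**What the plan says.** **Protocol.** Section 5.10 describes the first VLN exposure: "At screening, subjects will have an opportunity to smoke 2-3 VLN cigarettes over a 1-hour period". Section 5.1 places Screening "within 28 days prior to their first study visit at the start of Week -1". The footnote to the Summary of Study Events says "AE recording to begin immediately after the product trial at Screening". Section 6.4 defines an emergent AE as one "starting or worsening at the time of or after the first study product use (i.e., Product Trial" and states "However, only study product use-emergent AEs will be summarized". Section 5.12.11.2 reserves baseline signs and symptoms for events before the trial.

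**SAP.** Section 11.4 defines a product-use-emergent AE from study product administration, without naming the product trial, and attributes each event to a product by its onset date and time. The footnote to AE listing 16.2.7.1 assigns emergence to the last product used before onset.

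Tables 12-1, 14.3.1.1 and 14.3.1.2 have the columns *Baseline*, two VLN groups, two UB groups and *Overall*. Table 14.3.1.3 has the same categories as rows. All four carry the footnote "Overall includes AEs after the start of Week1 product use". For the earlier period, Table 12-1 says "Subjects used their own usual brand cigarettes at Week -1" and the post-text tables say "Subject used their usual brand at Baseline (Week -1". SAP 12 states that the analyses are aligned with the protocol.

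**The concern.** The protocol uses the trial as its tolerability check. It documents abnormal events such as excessive coughing, and subjects who react negatively do not continue. AEs at that point belong to the first VLN exposure, and the protocol makes them part of the emergent set to be summarized.

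The SAP's total begins at Week 1, and no column is named for the trial. A reader of the *Overall* figure would take it as the emergent AE frequency defined in the protocol, which it is not. If a trial AE is put under *Baseline*, the footnote invites the reader to connect it with usual-brand smoking. SAP 12 gives no warning of the difference.

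**Working it through.** The plan gives no figure to reproduce, so the check sets the time line and the subject counts against the table columns.

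**Inputs**
- Screening window: up to 28 days before the start of Week -1 (Protocol 5.1).
- Week -1: 7 days on usual brand; assignment on Day 1 of Week 1 (Protocol 2.1).
- Planned groups: VLN 50 + 50, UB 20 + 20 (Protocol 2.1).

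**Time line**
- Emergent time before *Overall* begins: up to 28 + 7 = 35 days.
- Part covered by *Baseline* as footnoted: Week -1, 7 days.
- Part with no described column: up to 35 − 7 = 28 days, from the trial to the start of Week -1.

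**Subjects**
- In the trial: 50 + 50 + 20 + 20 = 140.
- In a VLN group column: 50 + 50 = 100.
- Exposed to VLN in the trial but with no VLN column: 140 − 100 = 40.

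**Where could a product-trial AE go?**
1. *Under Baseline.* It is tabulated, but under a footnote that describes usual brand at Week -1. The word also clashes with the protocol, where baseline signs and symptoms come before the trial.
2. *In a VLN column, by onset time or last product used.* This is possible for the 100 subjects in the VLN groups. The 40 UB subjects have no such column, and an enrolled subject who leaves during Week -1 has no group at all. The shells also point the other way: they put Week -1 usual-brand AEs under *Baseline* and not in the UB columns, so the four group columns read as Week 1 onward.
3. *In no column.* An AE that the protocol says will be summarized is then missing from the tables.

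The *Overall* footnote excludes the event in all three cases. If the AE worsens after Week 1 begins, SAP 11.4 opens a new record that would count, but the original event still would not.

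**The case against.** The strongest reply is that a total starting at assignment is a sound layout. It avoids pooling screening VLN use, Week -1 usual-brand use and assigned-product use, and Protocol 6.4 prescribes neither an *Overall* column nor its window. That stands, provided the column is labelled as Week 1 onward and the protocol-defined emergent AEs are summarized somewhere. Neither is so at present.

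The SAP also says in section 14 that the shells may not reflect every aspect of the study. That weakens any inference from column layout, but the *Overall* restriction is an explicit rule repeated in four tables.

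Three stronger readings are tempting, and the documents do not support them:
- *Trial AEs are either left out or shown as usual-brand events.* A reader might infer this from the footnotes. But the column is headed *Baseline* and is separate from the UB columns, and the attribution rules in SAP 11.4 and the AE listing allow a VLN column for some subjects. Placement is undefined, not settled.
- *Nearly half of emergent time is lost.* A reader might set the 35 days against the 42 days of Weeks 1 to 6. That comparison uses the longest screening window, measures calendar time and not AEs or VLN exposure, counts 7 usual-brand days that have their own column, and ignores the follow-up call about 7 days after the last contact.
- *The data are lost.* Protocol 6.4 requires every event in the database to be listed, and Appendix 16.2.7.1 lists AEs of the safety population with onset date and time.

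**Conclusion.** The point holds as a conflict between Protocol 6.4 and the SAP's AE tables. Product-trial AEs of enrolled subjects are always excluded from *Overall*, their place among the other columns is undefined, and the departure is undeclared. At most 28 days per subject lack a described column. Any of the 140 planned subjects could have such an event, but only those who do are affected; the documents give no basis for estimating how many. The tables should be corrected, but this is a matter of tabulation and labelling: the events stay in the listing.

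A reader might also infer that correcting the tables would bring in the subjects least able to tolerate VLN. It would not. Those stopped at the trial do not continue, and the SAP safety population is limited to enrolled subjects. This assumes that enrolment takes place at Week -1, as the design sections of both documents indicate. Protocol 6.2 defines the safety population by smoking at least one VLN cigarette, so whether these subjects should be reported is a separate population question.

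**What to change.** In Tables 12-1, 14.3.1.1, 14.3.1.2 and 14.3.1.3:
- Replace *Baseline* with two categories: *VLN product trial (Screening to start of Week -1)* and *UB (Week -1)*. Give each its own denominator: safety-population subjects who smoked VLN in the trial, and those who smoked usual brand in Week -1.
- Either add a total of all emergent AEs from the product trial onward, or relabel the existing column *Overall, Week 1 onward*.

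In the text:
- Bring the SAP 11.4 definition into line with Protocol 6.4, or declare the difference in SAP 12.
- Note that AEs of subjects stopped at the product trial are outside the SAP safety population and so outside these tables.

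The cost is a change to shells, footnotes and one definition, plus a period flag derived from AE onset and visit dates. These dates are already collected, so no new data are needed.

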14.2 Figures Shells

Figures 14.2.2.1.1, 14.2.2.2.1, 14.2.6.1.1, 14.2.6.2.1, 14.2.6.3.1, 14.2.6.4.1, 14.2.6.5.1, 14.2.6.6.1, 14.2.6.7.1, 14.2.8.1, 14.2.8.4, 14.2.10.1.1, 14.2.10.2.1.1, 14.2.10.2.2.1, 14.2.10.3.1, and 14.2.10.4.1 will be in the following format:

[figure not shown]
Treatments B and C are shifted to the right for ease of reading

Program: /CAXXXX/sas_prg/pksas/adam_meangraph.sas DDMMYY HH:MM

Program: /CAXXXX/sas_prg/pksas/meangraph.sas DDMMYY HH:MM

Programmer's note: in the legend and footnotes, "Treatment" will be referred to as "Product" with the appropriate descriptions. The x-axis will be labeled "Time (Minutes)".

[figure not shown]
In-text Figures 11-1 through and 11-15 and post-text Figures 14.2.8.2, 14.2.8.5, 14.2.2.1.2, 14.2.2.2.2, 14.2.4.1 through 14.2.4.5, 14.2.6.1.2, 14.2.6.2.2, 14.2.6.3.2, 14.2.6.4.2, 14.2.6.5.2, 14.2.6.6.2, 14.2.6.7.2, 14.2.10.1.2, 14.2.10.2.1.2, 14.2.10.2.2.2, 14.2.10.3.2, and 14.2.10.4.2 will be presented in the following format:

Program: /CAXXXXX/sas_prg/pksas/adam_meangraph.sas DDMMYY HH:MM
Program: /CAXXXXX/sas_prg/pksas/meangraph.sas DDMMYY HH:MM

Programmer's note: in the legend and footnotes, "Treatment" will be referred to as "Product" with the appropriate descriptions. The x-axis will be labeled "Time (Minutes)".

Figures 14.2.8.3 and 14.2.8.6 will be presented in the following format:

Program: /CAXXXXX/sas_prg/pksas/adam_meangraph.sas DDMMMYYYY HH:MM
Program: /CAXXXXX/sas_prg/pksas/meangraph.sas DDMMMYYYY HH:MM

Programmer's note: in the legend and footnotes, "Treatment" will be referred to as "Product" with the appropriate descriptions. The x-axis will be labeled "Time (Minutes)".

14.3 Section 14 Summary Tables Shells

Post-text Table 14.1.1 will be in the following format:

Part 1 of X

Table 14.1.1 Summary of Disposition (Safety and PP Populations)

Population	Category	Study Product Group				Overall
		VLN Non-Mentholated	VLN Mentholated	UB Non-Mentholated	UB Mentholated	
Safety	Enrolled	XX (100%)	XX (100%)	XX (100%)	XX (100%)	XX (100%)
	Completed	XX (XX%)	XX (XX%)	XX (XX%)	XX (XX%)	XX (XX%)
	Discontinued Early	X (X%)	X (X%)	X (X%)	X (X%)	X (X%)
	<Reason1>	X (X%)	X (X%)	X (X%)	X (X%)	X (X%)
	<Reason2>	X (X%)	X (X%)	X (X%)	X (X%)	X (X%)
mITT	Enrolled	XX (100%)	XX (100%)	XX (100%)	XX (100%)	XX (100%)
	Completed	XX (XX%)	XX (XX%)	XX (XX%)	XX (XX%)	XX (XX%)
	Discontinued Early	X (X%)	X (X%)	X (X%)	X (X%)	X (X%)
	<Reason1>	X (X%)	X (X%)	X (X%)	X (X%)	X (X%)
	<Reason2>	X (X%)	X (X%)	X (X%)	X (X%)	X (X%)
PP	Enrolled	XX (100%)	XX (100%)	XX (100%)	XX (100%)	XX (100%)
	Completed	XX (XX%)	XX (XX%)	XX (XX%)	XX (XX%)	XX (XX%)
	Discontinued Early	X (X%)	X (X%)	X (X%)	X (X%)	X (X%)
	<Reason1>	X (X%)	X (X%)	X (X%)	X (X%)	X (X%)
	<Reason2>	X (X%)	X (X%)	X (X%)	X (X%)	X (X%)

Note: VLN non-mentholated = Non-mentholated VLN cigarettes

VLN mentholated = Mentholated VLN cigarettes

UB non-mentholated = Subjects' UB non-mentholated filtered cigarettes

UB mentholated = Subjects' UB mentholated filtered cigarettes

Program: /XAXXXX/ECR/sas_prg/stsas/tab_prog_name.sas DDMMYYYY HH:MM

Post-text Table 14.1.2 will be in the following format:

Page 1 of X

Table 14.1.2 Demographic Summary (Safety and PP Populations)

		Study Product Group				
		VLN	VLN	UB	UB	Overall
Population Trait		Non-Mentholated	Mentholated	Non-Mentholated	Mentholated	
Safety	Gender	Male	X (XX.X%)	X (XX.X%)	X (XX.X%)	X (XX.X%)
		Female	X (XX.X%)	X (XX.X%)	X (XX.X%)	X (XX.X%)
Race	American Indian		X (XX.X%)	X (XX.X%)	X (XX.X%)	X (XX.X%)
	Asian		X (XX.X%)	X (XX.X%)	X (XX.X%)	X (XX.X%)
	Black		X (XX.X%)	X (XX.X%)	X (XX.X%)	X (XX.X%)
Age* (yrs)	n		X	X	X	X
	Mean		X.X	X.X	X.X	X.X
	SD		X.XX	X.XX	X.XX	X.XX
	Minimum		XX	XX	XX	XX
	Median		X.X	X.X	X.X	X.X
	Maximum		XX	XX	XX	XX
Weight (kg)	n		X	X	X	X
	Mean		X.X	X.X	X.X	X.X
	SD		X.XX	X.XX	X.XX	X.XX
	Minimum		XX	XX	XX	XX
	Median		X.X	X.X	X.X	X.X
	Maximum		XX	XX	XX	XX
Height (cm)	n		X	X	X	X
	Mean		XX.XX	XX.XX	XX.XX	XX.XX
	SD		X.XXX	X.XXX	X.XXX	X.XXX
	Minimum		XX.X	XX.X	XX.X	XX.X
	Median		XX.XX	XX.XX	XX.XX	XX.XX
	Maximum		XX.X	XX.X	XX.X	XX.X

Note: * Age is derived from birth date to date of informed consent.

VLN non-mentholated = Non-mentholated VLN cigarettes

VLN mentholated = Mentholated VLN cigarettes

UB non-mentholated = Subjects' UB non-mentholated filtered cigarettes
UB mentholated = Subjects' UB mentholated filtered cigarettes

Program: /CAXXXX/ECR/sas_prg/stsas/tab programname.sas DDMMYYYY HH:MM

Programmer Note: Summary for ITT and PP population will also be presented in the table.

Post-text Table 14.1.3 will be in the following format:

Page 1 of X

Table 14.1.3 Tobacco/Nicotine Product Use History Summary (Safety and PP Populations)

Population Trait		Study Product Group					Overall
		VLN Non-Mentholated	UB Non-Mentholated	VLN Mentholated	UB Mentholated		
Safety	Brand	XXXXX	X (XX.X%)	X (XX.X%)	X (XX.X%)	X (XX.X%)	X (XX.X%)
		XXXXXX	X (XX.X%)	X (XX.X%)	X (XX.X%)	X (XX.X%)	X (XX.X%)
	Brand Style	XXXXX	X (XX.X%)	X (XX.X%)	X (XX.X%)	X (XX.X%)	X (XX.X%)
		XXXXXX	X (XX.X%)	X (XX.X%)	X (XX.X%)	X (XX.X%)	X (XX.X%)
	Flavor	XXXXX	X (XX.X%)	X (XX.X%)	X (XX.X%)	X (XX.X%)	X (XX.X%)
		XXXXXX	X (XX.X%)	X (XX.X%)	X (XX.X%)	X (XX.X%)	X (XX.X%)
	Size	XXXXX	X (XX.X%)	X (XX.X%)	X (XX.X%)	X (XX.X%)	X (XX.X%)
		XXXXXX	X (XX.X%)	X (XX.X%)	X (XX.X%)	X (XX.X%)	X (XX.X%)
Duration (yrs)	n		X	X	X	X	X
	Mean		X.X	X.X	X.X	X.X	X.X
	SD		X.XX	X.XX	X.XX	X.XX	X.XX
	Minimum		XX	XX	XX	XX	XX
	Median		X.X	X.X	X.X	X.X	X.X
	Maximum		XX	XX	XX	XX	XX
CPD	n		X	X	X	X	X
	Mean		X.X	X.X	X.X	X.X	X.X
	SD		X.XX	X.XX	X.XX	X.XX	X.XX
	Minimum		XX	XX	XX	XX	XX
	Median		X.X	X.X	X.X	X.X	X.X
	Maximum		XX	XX	XX	XX	XX

Note: CPD = Cigarettes per day

VLN non-mentholated = Non-mentholated VLN cigarettes

VLN mentholated = Mentholated VLN cigarettes

UB non-mentholated = Subjects' UB non-mentholated filtered cigarettes

UB mentholated = Subjects' UB mentholated filtered cigarettes

Program: /CAXXXXX/ECR/sas_prg/stsas/tab programname.sas DDMMYYYY HH:MM

Programmer Note: Summary for ITT and PP population will also be presented in the table.

Post-text Tables 14.2.1.1.1-2 and 14.2.1.2.1-2 will be in the following format:

Page 1 of X
 Table 14.2.1.1.1.1 Summary of Number of Cigarettes Smoked per Week by Study Product Group and Study Week
 (PP Population)

Study Week	Statistics	Study Product Group					
		VLN Non-Menthолated	VLN Menthолated	VLN Combined	UB Non-Menthолated	UB Menthолated	UB Combined
Week -1*	n	X	X	X	X	X	X
	Mean	X.X	X.X	X.X	X.X	X.X	X.X
	SD	X.XX	X.XX	X.XX	X.XX	X.XX	X.XX
	CV%	XX.X	XX.X	XX.X	XX.X	XX.X	XX.X
	SEM	X.XX	X.XX	X.XX	X.XX	X.XX	X.XX
	Minimum	XX	XX	XX	XX	XX	XX
	Median	X.X	X.X	X.X	X.X	X.X	X.X
	Maximum	XX	XX	XX	XX	XX	XX
Week 1	n	X	X	X	X	X	X
	Mean	X.X	X.X	X.X	X.X	X.X	X.X
	SD	X.XX	X.XX	X.XX	X.XX	X.XX	X.XX
	CV%	XX.X	XX.X	XX.X	XX.X	XX.X	XX.X
	SEM	X.XX	X.XX	X.XX	X.XX	X.XX	X.XX
	Minimum	XX	XX	XX	XX	XX	XX
	Median	X.X	X.X	X.X	X.X	X.X	X.X
	Maximum	XX	XX	XX	XX	XX	XX

Note: *Subjects used their own usual brand cigarettes at Week -1.

VLN non-mentholated = Non-mentholated VLN cigarettes

VLN mentholated = Mentholated VLN cigarettes

UB non-mentholated = Subjects' UB non-mentholated filtered cigarettes

UB mentholated = Subjects' UB mentholated filtered cigarettes

Program: /CAXXXXX/ECR/sas_prg/stsas/tab programname.sas DDMMYYYY HH:MM

Programmer Note: All study weeks will be presented in the table.

Post-text Tables 14.2.1.1.2 and 14.2.1.2.2 will be in the following format:

Page 1 of X

Table 14.2.1.1.2 Statistical Comparison of Number of Cigarettes Smoked per Week at Weeks 2 and 6 Versus Week -1
 by Study Product Group (PP Population)

Study Week	Product Group	Means		Difference (Test Week - Baseline)	XX% Confidence Interval	p-value
		Test Week	Baseline			
Week 2	VLN Non-Mentholated	XXX	XXX	XXX	XXX - XXX	X.XXXX
	VLN Mentholated	XXX	XXX	XXX	XXX - XXX	X.XXXX
	VLN Combined	XXX	XXX	XXX	XXX - XXX	X.XXXX
	UB Non-Mentholated	XXX	XXX	XXX	XXX - XXX	X.XXXX
	UB Mentholated	XXX	XXX	XXX	XXX - XXX	X.XXXX
	UB Combined	XXX	XXX	XXX	XXX - XXX	X.XXXX
Week 6	VLN Non-Mentholated	XXX	XXX	XXX	XXX - XXX	X.XXXX
	VLN Mentholated	XXX	XXX	XXX	XXX - XXX	X.XXXX
	VLN Combined	XXX	XXX	XXX	XXX - XXX	X.XXXX
	UB Non-Mentholated	XXX	XXX	XXX	XXX - XXX	X.XXXX
	UB Mentholated	XXX	XXX	XXX	XXX - XXX	X.XXXX
	UB Combined	XXX	XXX	XXX	XXX - XXX	X.XXXX

Note: Baseline = Week -1
 Subjects used their own usual brand cigarettes at Week -1.
 VLN non-mentholated = Non-mentholated VLN cigarettes
 VLN mentholated = Mentholated VLN cigarettes
 UB non-mentholated = Subjects' UB non-mentholated filtered cigarettes
 UB mentholated = Subjects' UB mentholated filtered cigarettes
 Paired t-test method is used to perform the analysis.

Program: /CAXXXXXX/ECR/sas_prg/stsas/tab programname.sas DDMMYYYY HH:MM

Post-text Tables 14.2.1.1.3 and 14.2.1.2.3 will be in the following format:

Page 1 of X

Table 14.2.1.1.3 Statistical Comparison of Number of Cigarettes Smoked per Week Among Study Product Groups
 at Weeks 2 and 6 (PP Population)

Study Week	Comparison	LSMeans		LSMean Difference (Test - Reference)	XX% Confidence Interval	p-value
		Test (n)	Reference (n)			
Week 2	VLN Non-mentholated vs UB Non-mentholated	X.XX (X)	X.XX (X)	XXX.XX	XX.XX - XXX.XX	X.XXXX
	VLN Mentholated vs UB Mentholated	X.XX (X)	X.XX (X)	XXX.XX	XX.XX - XXX.XX	X.XXXX
	VLN Combined vs UB Combined	X.XX (X)	X.XX (X)	XXX.XX	XX.XX - XXX.XX	X.XXXX
Week 6	VLN Non-mentholated vs UB Non-mentholated	X.XX (X)	X.XX (X)	XXX.XX	XX.XX - XXX.XX	X.XXXX
	VLN Mentholated vs UB Mentholated	X.XX (X)	X.XX (X)	XXX.XX	XX.XX - XXX.XX	X.XXXX
	VLN Combined vs UB Combined	X.XX (X)	X.XX (X)	XXX.XX	XX.XX - XXX.XX	X.XXXX

Note: LSMeans, LSmean difference, CI and p-values are from the ANOVA.
 n = Number of observation used in the analysis

Test = The first product in the comparison

Reference = The second product in the comparison

VLN non-mentholated = Non-mentholated VLN cigarettes

VLN mentholated = Mentholated VLN cigarettes

UB non-mentholated = Subjects' UB non-mentholated filtered cigarettes

UB mentholated = Subjects' UB mentholated filtered cigarettes

Program: /CAXXXX/ECR/sas_prg/stsas/tab programname.sas DDMMYYYY HH:MM

Post-text Tables 14.2.3.1.1-2 will be in the following format:

Page 1 of X
 Table 14.2.3.1.1 Summary of Puff Topography Parameters by Study Product Group and Study Week (PP Population)

Parameter(unit)	Study Week	Study Product Group					
		VLN Non-Menth	VLN Menth	VLN Combined	UB Non-Menth	UB Menth	UB Combined
Puff Duration (XX)	Week -1*	n	X	X	X	X	X
		Mean	X.X	X.X	X.X	X.X	X.X
		SD	X.XX	X.XX	X.XX	X.XX	X.XX
		CV%	XX.X	XX.X	XX.X	XX.X	XX.X
		SEM	X.XX	X.XX	X.XX	X.XX	X.XX
		Minimum	XX	XX	XX	XX	XX
		Median	X.X	X.X	X.X	X.X	X.X
		Maximum	XX	XX	XX	XX	XX
	Week 2	n	X	X	X	X	X
		Mean	X.X	X.X	X.X	X.X	X.X
		SD	X.XX	X.XX	X.XX	X.XX	X.XX
		CV%	XX.X	XX.X	XX.X	XX.X	XX.X
		SEM	X.XX	X.XX	X.XX	X.XX	X.XX
		Minimum	XX	XX	XX	XX	XX
		Median	X.X	X.X	X.X	X.X	X.X
		Maximum	XX	XX	XX	XX	XX

Note: *Subjects used their own usual brand cigarettes at Week -1.

VLN non-mentholated = Non-mentholated VLN cigarettes

VLN mentholated = Mentholated VLN cigarettes

UB non-mentholated = Subjects' UB non-mentholated filtered cigarettes

UB mentholated = Subjects' UB mentholated filtered cigarettes

Program: /CAXXXXX/ECR/sas_prg/stsas/tab programname.sas DDMMYYYY HH:MM

Programmer Note: Study Week 6 and other topography parameters will also be presented in the table.

Post-text Table 14.2.3.2 will be in the following format:

Page 1 of X

Table 14.2.3.2 Statistical Comparison of Puff Topography Parameters at Weeks 2 and 6 Versus Week -1 by Study Product Group (PP Population)

Parameter(unit)	Study Week	Product Group	Means		Difference (Test Week - Baseline)	XX% Confidence Interval	p-value
			Test	Week			
Puff Duration (XX)	Week 2	VLN Non-Mentholated	XXX	XXX	XXX	XXX - XXX	X.XXXX
		VLN Mentholated	XXX	XXX	XXX	XXX - XXX	X.XXXX
		VLN Combined	XXX	XXX	XXX	XXX - XXX	X.XXXX
		UB Non-Mentholated	XXX	XXX	XXX	XXX - XXX	X.XXXX
		UB Mentholated	XXX	XXX	XXX	XXX - XXX	X.XXXX
		UB Combined	XXX	XXX	XXX	XXX - XXX	X.XXXX
	Week 6	VLN Non-Mentholated	XXX	XXX	XXX	XXX - XXX	X.XXXX
		VLN Mentholated	XXX	XXX	XXX	XXX - XXX	X.XXXX
		VLN Combined	XXX	XXX	XXX	XXX - XXX	X.XXXX
		UB Non-Mentholated	XXX	XXX	XXX	XXX - XXX	X.XXXX
		UB Mentholated	XXX	XXX	XXX	XXX - XXX	X.XXXX
		UB Combined	XXX	XXX	XXX	XXX - XXX	X.XXXX

Note: Baseline = Week -1

Subjects used their own usual brand cigarettes at Week -1.

VLN non-mentholated = Non-mentholated VLN cigarettes

VLN mentholated = Mentholated VLN cigarettes

UB non-mentholated = Subjects' UB non-mentholated filtered cigarettes

UB mentholated = Subjects' UB mentholated filtered cigarettes

Paired t-test method is used to perform the analysis.

Program: /CAXXXXX/ECR/sas_prg/stsas/tab programname.sas DDMMYY YYYY HH:MM

Programmer Note: Other topography parameters will also be presented in the table.

Post-text Table 14.2.3.3 will be in the following format:

Page 1 of X

Table 14.2.3.3 Statistical Comparison of Puff Topography Parameters Among Study Product Groups at Weeks 2 and 6
 (PP Population)

Parameter(unit)	Study Week	Comparison	LSMeans		LSMean Difference (Test - Reference)	XX% Confidence Interval	p-value
			Test (n)	Reference (n)			
Puff Duration (XX)	Week 2	VLN Non-mentholated vs UB Non-mentholated	X.XX (X)	X.XX (X)	XXX.XX	XX.XX - XXX.XX	X.XXXX
		VLN Mentholated vs UB Mentholated	X.XX (X)	X.XX (X)	XXX.XX	XX.XX - XXX.XX	X.XXXX
		VLN Combined vs UB Combined	X.XX (X)	X.XX (X)	XXX.XX	XX.XX - XXX.XX	X.XXXX
	Week 6	VLN Non-mentholated vs UB Non-mentholated	X.XX (X)	X.XX (X)	XXX.XX	XX.XX - XXX.XX	X.XXXX
		VLN Mentholated vs UB Mentholated	X.XX (X)	X.XX (X)	XXX.XX	XX.XX - XXX.XX	X.XXXX
		VLN Combined vs UB Combined	X.XX (X)	X.XX (X)	XXX.XX	XX.XX - XXX.XX	X.XXXX

Note: LSMeans, LSmean difference, CI and p-values are from the ANOVA.
 n = Number of observation used in the analysis

Test = The first product in the comparison

Reference = The second product in the comparison

VLN non-mentholated = Non-mentholated VLN cigarettes

VLN mentholated = Mentholated VLN cigarettes

UB non-mentholated = Subjects' UB non-mentholated filtered cigarettes

UB mentholated = Subjects' UB mentholated filtered cigarettes

Program: /CAXXXXX/ECR/sas_prg/stsas/tab programname.sas DDMMYYYY HH:MM

Programmer Note: Other topography parameters will also be presented in the table.

Post-text Tables 14.2.5.1.1.1.1-2, 14.2.5.1.1.4.1-2, 14.2.5.2.1.1.1-2, 14.2.5.2.1.4.1-2, 14.2.5.3.1.1.1-2, 14.2.5.3.1.4.1-2, 14.2.5.4.1.1.1-2, 14.2.5.4.1.4.1-2, 14.2.5.5.1.1.1-2, 14.2.5.5.1.4.1-2, 14.2.5.6.1.1.1-2, 14.2.5.6.1.4.1-2, and 14.2.5.7.1.1.1-2 will be in the following format:

Page 1 of X

Table 14.2.5.1.1.1.1 Summary of Urinary NNAL Mass Excreted (unit) by Study Product Group and Study Week
(PP Population)

Study Week	Statistics	Study Product Group					
		VLN Non-Menthолated	VLN Menthолated	VLN Combined	UB Non-Menthолated	UB Menthолated	UB Combined
Week -1*	n	X	X	X	X	X	X
	Mean	X.X	X.X	X.X	X.X	X.X	X.X
	SD	X.XX	X.XX	X.XX	X.XX	X.XX	X.XX
	CV%	XX.X	XX.X	XX.X	XX.X	XX.X	XX.X
	SEM	X.XX	X.XX	X.XX	X.XX	X.XX	X.XX
	Minimum	XX	XX	XX	XX	XX	XX
	Median	X.X	X.X	X.X	X.X	X.X	X.X
	Maximum	XX	XX	XX	XX	XX	XX
Week 2	n	X	X	X	X	X	X
	Mean	X.X	X.X	X.X	X.X	X.X	X.X
	SD	X.XX	X.XX	X.XX	X.XX	X.XX	X.XX
	CV%	XX.X	XX.X	XX.X	XX.X	XX.X	XX.X
	SEM	X.XX	X.XX	X.XX	X.XX	X.XX	X.XX
	Minimum	XX	XX	XX	XX	XX	XX
	Median	X.X	X.X	X.X	X.X	X.X	X.X
	Maximum	XX	XX	XX	XX	XX	XX

Note: *Subjects used their own usual brand cigarettes at Week -1.

VLN non-mentholated = Non-mentholated VLN cigarettes

VLN mentholated = Menthолated VLN cigarettes

UB non-mentholated = Subjects' UB non-mentholated filtered cigarettes

UB mentholated = Subjects' UB mentholated filtered cigarettes

Program: /CAXXXX/ECR/sas_prg/stsas/tab programname.sas DDMMYYYY HH:MM

Programmer Note: Week 6 will also be presented in the table.

22nd Century Group, Inc

VLN Cigarettes

Celerion, Clinical Study Report No. CA24914

Post-text Tables 14.2.5.1.1.2.1-2, 14.2.5.1.1.3.1-2, 14.2.5.1.1.5.1-2, 14.2.5.1.1.6.1-2, 14.2.5.2.1.2.1-2, 14.2.5.2.1.3.1-2, 14.2.5.2.1.5.1-2, 14.2.5.2.1.6.1-2, 14.2.5.3.1.2.1-2, 14.2.5.3.1.3.1-2, 14.2.5.3.1.5.1-2, 14.2.5.3.1.6.1-2, 14.2.5.4.1.2.1-2, 14.2.5.4.1.3.1-2, 14.2.5.4.1.5.1-2, 14.2.5.4.1.6.1-2, 14.2.5.5.1.2.1-2, 14.2.5.5.1.3.1-2, 14.2.5.5.1.5.1-2, 14.2.5.5.1.6.1-2, 14.2.5.6.1.2.1-2, 14.2.5.6.1.3.1-2, 14.2.5.6.1.5.1-2, 14.2.5.6.1.6.1-2, 14.2.5.7.1.2.1-2, and 14.2.5.7.3.1-2 will be in the following format:

Page 1 of X

Table 14.2.5.1.1.2.1 Summary of Urinary NNAL Mass Excreted Change from Baseline (unit)
by Study Product Group and Study Week (PP Population)

Study Week	Statistics	Study Product Group					
		VLN Non-Mentholated	VLN Mentholated	VLN Combined	UB Non-Mentholated	UB Mentholated	UB Combined
Week 2	n	X	X	X	X	X	X
	Mean	X.X	X.X	X.X	X.X	X.X	X.X
	SD	X.XX	X.XX	X.XX	X.XX	X.XX	X.XX
	CV%	XX.X	XX.X	XX.X	XX.X	XX.X	XX.X
	SEM	X.XX	X.XX	X.XX	X.XX	X.XX	X.XX
	Minimum	XX	XX	XX	XX	XX	XX
	Median	X.X	X.X	X.X	X.X	X.X	X.X
	Maximum	XX	XX	XX	XX	XX	XX
Week 6	n	X	X	X	X	X	X
	Mean	X.X	X.X	X.X	X.X	X.X	X.X
	SD	X.XX	X.XX	X.XX	X.XX	X.XX	X.XX
	CV%	XX.X	XX.X	XX.X	XX.X	XX.X	XX.X
	SEM	X.XX	X.XX	X.XX	X.XX	X.XX	X.XX
	Minimum	XX	XX	XX	XX	XX	XX
	Median	X.X	X.X	X.X	X.X	X.X	X.X
	Maximum	XX	XX	XX	XX	XX	XX

Note: Baseline = Week -1

Subjects used their own usual brand cigarettes at Week -1.

VLN non-mentholated = Non-mentholated VLN cigarettes

VLN mentholated = Mentholated VLN cigarettes

UB non-mentholated = Subjects' UB non-mentholated filtered cigarettes

UB mentholated = Subjects' UB mentholated filtered cigarettes

22nd Century Group, Inc
VLN Cigarettes
Celerion, Clinical Study Report No. CA24914

Program: /CAXXXXX/ECR/sas_prg/stsas/tab programname.sas DDMMYYYY HH:MM

Post-text Tables 14.2.5.1.2, 14.2.5.2.2, 14.2.5.3.2, 14.2.5.4.2, 14.2.5.5.2, 14.2.5.6.2, and 14.2.5.7.2 will be in the following format:

Page 1 of X

Table 14.2.5.1.2 Statistical Comparison of Urinary NNAL Mass Excreted (unit) at Weeks 2 and 6 Versus Week -1
 by Study Product Group (PP Population)

Study Week	Product Group	Means		Difference (Test Week - Baseline)	XX% Confidence Interval	p-value
		Test Week	Baseline			
<hr/>						
Week 2	VLN Non-Mentholated	XXX	XXX	XXX	XXX - XXX	X.XXXX
	VLN Mentholated	XXX	XXX	XXX	XXX - XXX	X.XXXX
	VLN Combined	XXX	XXX	XXX	XXX - XXX	X.XXXX
	UB Non-Mentholated	XXX	XXX	XXX	XXX - XXX	X.XXXX
	UB Mentholated	XXX	XXX	XXX	XXX - XXX	X.XXXX
	UB Combined	XXX	XXX	XXX	XXX - XXX	X.XXXX
<hr/>						
Week 6	VLN Non-Mentholated	XXX	XXX	XXX	XXX - XXX	X.XXXX
	VLN Mentholated	XXX	XXX	XXX	XXX - XXX	X.XXXX
	VLN Combined	XXX	XXX	XXX	XXX - XXX	X.XXXX
	UB Non-Mentholated	XXX	XXX	XXX	XXX - XXX	X.XXXX
	UB Mentholated	XXX	XXX	XXX	XXX - XXX	X.XXXX
	UB Combined	XXX	XXX	XXX	XXX - XXX	X.XXXX
<hr/>						

Note: Baseline = Week -1

Subjects used their own usual brand cigarettes at Week -1.

VLN non-mentholated = Non-mentholated VLN cigarettes

VLN mentholated = Mentholated VLN cigarettes

UB non-mentholated = Subjects' UB non-mentholated filtered cigarettes

UB mentholated = Subjects' UB mentholated filtered cigarettes

Paired t-test method is used to perform the analysis.

Program: /CAXXXXXX/ECR/sas_prg/stsas/tab programname.sas DDMMYYYY HH:MM

Post-text Tables 14.2.5.1.3, 14.2.5.2.3, 14.2.5.3.3, 14.2.5.4.3, 14.2.5.5.3, 14.2.5.6.3, and 14.2.5.7.3 will be in the following format:

Page 1 of X

Table 14.2.5.1.3 Statistical Comparison of Urinary NNAL Mass Excreted (unit) Among Study Product Groups
 at Weeks 2 and 6 (PP Population)

Study Week	Comparison	LSMeans		LSMean Difference (Test - Reference)	XX% Confidence Interval	p-value
		Test (n)	Reference (n)			
Week 2	VLN Non-mentholated vs UB Non-mentholated	X.XX (X)	X.XX (X)	XXX.XX	XX.XX - XXX.XX	X.XXXX
	VLN Mentholated vs UB Mentholated	X.XX (X)	X.XX (X)	XXX.XX	XX.XX - XXX.XX	X.XXXX
	VLN Combined vs UB Combined	X.XX (X)	X.XX (X)	XXX.XX	XX.XX - XXX.XX	X.XXXX
Week 6	VLN Non-mentholated vs UB Non-mentholated	X.XX (X)	X.XX (X)	XXX.XX	XX.XX - XXX.XX	X.XXXX
	VLN Mentholated vs UB Mentholated	X.XX (X)	X.XX (X)	XXX.XX	XX.XX - XXX.XX	X.XXXX
	VLN Combined vs UB Combined	X.XX (X)	X.XX (X)	XXX.XX	XX.XX - XXX.XX	X.XXXX

Note: LSMeans, LSmean difference, CI and p-values are from the ANOVA.
 n = Number of observation used in the analysis

Test = The first product in the comparison

Reference = The second product in the comparison

VLN non-mentholated = Non-mentholated VLN cigarettes

VLN mentholated = Mentholated VLN cigarettes

UB Non-mentholated = Subjects' UB non-mentholated filtered cigarettes

UB mentholated = Subjects' UB mentholated filtered cigarettes

Program: /CAXXXXXX/ECR/sas_prg/stsas/tab programname.sas DDMMYYYY HH:MM

Post-text Tables 14.2.7.1.1 through 14.2.7.4.2 will be in the following format:

Page 1 of X

Table 14.2.7.1.1 Unadjusted Plasma Nicotine Concentrations (ng/mL) Following Use of UB Non-Mentholated Filtered Cigarettes and Non-Mentholated VLN Cigarettes (Pharmacokinetic Population from PP)

Subject Number	Sample Times (min)									
	XX	XX	XX	XX	XX	XX	XX	XX	XX	XX
X	BLQ	XX								
X	BLQ	XX								
X	BLQ	XX								
n	XX	XX	XX	XX	XX	XX	XX	XX	XX	XX
Mean	XX.X	XX.X	XX.X	XX.X	XX.X	XX.X	XX.X	XX.X	XX.X	XX.X
SD	XX.XX	XX.XX	XX.XX	XX.XX	XX.XX	XX.XX	XX.XX	XX.XX	XX.XX	XX.XX
CV%	.	XX.X								
SEM	XX.XX	XX.XX	XX.XX	XX.XX	XX.XX	XX.XX	XX.XX	XX.XX	XX.XX	XX.XX
Minimum	XX	XX	XX	XX	XX	XX	XX	XX	XX	XX
Median	XX.X	XX.X	XX.X	XX.X	XX.X	XX.X	XX.X	XX.X	XX.X	XX.X
Maximum	XX	XX	XX	XX	XX	XX	XX	XX	XX	XX

